### 9.3 Definitions

#### 9.3.1 Adverse Event

An adverse event is any unfavorable and unintended sign (including a clinically-significant abnormal laboratory finding, for example), symptom, or disease temporally associated with the study or use of investigational drug product, whether or not the AE is considered related to the investigational drug product.

#### 9.3.2 Adverse Reaction and Suspected Adverse Reaction

An adverse reaction is any AE caused by the Study Drug.

A suspected adverse reaction is any AE for which there is a reasonable possibility that the drug caused the AE. A suspected adverse reaction implies a lesser degree of certainty about causality than an adverse reaction.

#### 9.3.3 Serious Adverse Event (SAE)

A SAE is any AE that in the view of either the Investigator or Sponsor, meets any of the following criteria:

- Results in death
- Is life threatening, that is, poses an immediate risk of death at the time of the event
- An AE or suspected adverse reaction is considered “life-threatening” if, in the view of either the Investigator or Sponsor, its occurrence places the patient at immediate risk of death. It does not include an AE or suspected adverse reaction that, had it occurred in a more severe form, might have caused death
- Requires inpatient hospitalization or prolongation of existing hospitalization
- Results in a persistent or significant incapacity or substantial disruption of the ability to conduct normal life functions
- Results in a congenital anomaly or birth defect in the offspring of the patient (whether the patient is male or female)
- Important medical events that may not result in death, are not life-threatening, or do not require hospitalization may also be considered serious when, based upon appropriate medical judgment, they may jeopardize the patient and may require medical or surgical intervention to prevent one of the outcomes listed in this definition. Examples of such medical events include allergic bronchospasm requiring intensive treatment in an emergency room or at home, blood dyscrasias or convulsions that do not result in inpatient hospitalization, or the development of drug dependency or drug abuse

### **9.3.3.1 Adverse Events of Special Interest**

For the purpose of this study severe reductions in platelet count  $< 50,000 \text{ mm}^3$  are considered as AE of special interest and should be subject to expediting reporting to the Sponsor following the same requirements as for SAE reporting (Section 9.4.1).

## **9.4 Monitoring and Recording Adverse Events**

Any pre-existing conditions or signs and/or symptoms present in a patient prior to the start of the study (i.e., before informed consent) should be recorded as Medical History and not recorded as AEs unless the pre-existing condition worsened. The Investigator should always group signs and symptoms into a single term that constitutes a **single unifying diagnosis** if possible.

### **9.4.1 Serious Adverse Events/Adverse Events of Special Interest**

In the interest of patient safety, and in order to fulfill regulatory requirements, all SAEs and AEs of special interest (regardless of their relationship to Study Drug) should be reported to the Sponsor or designee within 24 hours of the Study Center's first knowledge of the event. The collection of SAEs will begin after the patient signs the informed consent form and stop at the end of the patient's follow-up period. When the Investigator is reporting by telephone, it is important to speak to someone in person versus leaving a message. An Initial Serious Adverse Event Form should be completed and a copy should be emailed or faxed to the Sponsor or designee. The contact information for reporting SAEs is as follows:

**Attention:** [REDACTED]

**Email:** [REDACTED]

**Fax:** [REDACTED]

Detailed information should be actively sought and included on Follow-Up Serious Adverse Event Forms as soon as additional information becomes available. All SAEs will be followed until resolution during the study period. SAEs that remain ongoing past the patient's last protocol-specified follow-up visit will be evaluated by the Investigator and Sponsor. If the Investigator and Sponsor agree the patient's condition is unlikely to resolve, the Investigator and Sponsor will determine the follow-up requirement.

All SAEs considered treatment-related, as defined in [Section 9.4.3.1](#), will be reported by the Sponsor to the DSMB as described in [Section 3.6](#).

### **9.4.2 Non-Serious Adverse Events**

The recording of non-serious AEs will begin after the patient signs the informed consent form and will stop at the end of the patient's follow-up period. The Investigator will monitor each patient closely and record all observed or volunteered AEs on the Adverse Event Case Report Form.

### **9.4.3 Evaluation of Adverse Events (Serious and Non-Serious)**

The Investigator's opinion of the following should be documented on the Adverse Event Case Report Form:

#### **9.4.3.1 Relationship to the Study Drug**

The event's relationship to the Study Drug (ISIS 681257 or placebo) is characterized by 1 of the following:

- **Related:** There is clear evidence that the event is related to the use of Study Drug, e.g., confirmation by positive re-challenge test
- **Possible:** The event cannot be explained by the patient's medical condition, concomitant therapy, or other causes, and there is a plausible temporal relationship between the event and Study Drug (ISIS 681257 or placebo) administration
- **Unlikely/Remote:** An event for which an alternative explanation is more likely (e.g., concomitant medications or ongoing medical conditions. For reporting purposes, Unlikely/Remote will be grouped together with Not Related)
- **Not Related:** The event can be readily explained by the patient's underlying medical condition, concomitant therapy, or other causes, and therefore, the Investigator believes no relationship exists between the event and Study Drug

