### 5.1 Inclusion Criteria

1. Must have given written informed consent (signed and dated) and any authorizations required by local law and be able to comply with all study requirements
2. Males or females aged  $\geq 18$  and  $\leq 80$  years old at the time of informed consent
3. Clinical diagnosis of CVD defined as documented coronary artery disease (CAD), stroke, or peripheral artery disease
4. Lp(a) plasma level  $\geq 60$  mg/dL
5. Must be on standard-of-care preventative therapy for other than elevated Lp(a) CVD risk factors
6. Patients on the following medications must be on a stable regimen for at least 4 weeks prior to Screening and expected to remain on a stable regimen through the end of the post-treatment follow-up period:
  - a. lipid lowering drugs (statins, ezetimibe, proprotein convertase subtilisin/kexin type 9 [PCSK9s] inhibitors, niacin, fibrates, fish oil or other products containing omega-3 fatty acids including OTC preparations)
  - b. antiplatelet drugs
  - c. testosterone, estrogens, progesterone, growth hormone or progestins

7. Females: must be non-pregnant and non-lactating and either:
  - a. surgically sterile (e.g., tubal occlusion, hysterectomy, bilateral salpingectomy, bilateral oophorectomy)
  - b. post-menopausal (defined as 12 months of spontaneous amenorrhea in females > 55 years of age or, in females ≤ 55 years, 12 months of spontaneous amenorrhea without an alternative medical cause and FSH levels in the postmenopausal range for the laboratory involved)
  - c. Abstinent\* or
  - d. if engaged in sexual relations of child-bearing potential, agree to use 2 highly effective contraceptive methods (refer to [Section 6.3.1](#)) from the time of signing the informed consent form until at least 16 weeks after the last dose of Study Drug (ISIS 681257 or placebo)

\* Abstinence is only acceptable as true abstinence, i.e., when this is in line with the preferred and usual lifestyle of the patient. Periodic abstinence (e.g., calendar, ovulation, symptothermal, post-ovulation methods), declaration of abstinence for the duration of a trial and withdrawal are not acceptable methods of contraception
8. Males must be surgically sterile or, if engaged in sexual relations with a female of child-bearing potential, the patient must be using an acceptable contraceptive method (refer to [Section 6.3.1](#)) from the time of signing the informed consent form until at least 16 weeks after the last dose of ISIS 681257

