### **10.1.4 Dose Selection**

Dose selection for the further development will be based on the following efficacy and safety considerations; more than 1 dose may meet these criteria. An effective dose, or dose regimen, will be one that achieves clinically-meaningful reduction in plasma Lp(a) levels. Safety will be evaluated on the basis of incidence of expected and unexpected treatment-related SAEs and other specific safety considerations including the incidence of platelet reductions, and renal or hepatic injury.

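### Section 9.4.3.1 limits *Possible* to events with no other explanation, which conflicts with 9.3.2 and leaves no category for competing causes, so some drug-caused SAEs may miss the 48-hour DSMB notice and the treatment-related dose-selection criterion

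*Protocol*

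**What the plan says.** Section 9.4.3.1 of the protocol (Amendment 4; the Amendment 3 text in the same file is identical here) gives the investigator four choices for relationship to Study Drug:

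- *Related*: the link to Study Drug is clearly shown; a positive re-challenge is the example given.
- *Possible*: "The event cannot be explained by the patient's medical condition, concomitant therapy, or other causes, and there is a plausible temporal relationship" with administration of Study Drug.
- *Unlikely/Remote*: "An event for which an alternative explanation is more likely". The section adds: "For reporting purposes, Unlikely/Remote will be grouped together with Not Related".
- *Not Related*: disease, concomitant therapy or another cause readily explains the event, and the investigator believes that there is no relationship.

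Section 9.3.2 uses a different standard: "A suspected adverse reaction is any AE for which there is a reasonable possibility that the drug caused the AE".

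Section 5.1 requires documented cardiovascular disease and, in criterion 5: "Must be on standard-of-care preventative therapy for other than elevated Lp(a) CVD risk factors".

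Two decisions use the rating directly. Section 9.4.1 says that "All SAEs considered treatment-related, as defined in" Section 9.4.3.1 are reported by the Sponsor to the DSMB in the way set out in Section 3.6. Section 10.1.4, on choosing the dose, says: "Safety will be evaluated on the basis of incidence of expected and unexpected treatment-related SAEs". Section 10.6.2.1 also plans separate summaries of treatment-emergent events and serious events potentially related to Study Drug.

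**The concern.** A reasonable possibility that a drug caused an event can coexist with another explanation. The *Possible* definition rules that out, because any available explanation from disease or background therapy is enough to fail it. *Related* does not fill the gap, since it asks for clear evidence of the kind that a positive re-challenge gives.

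In this population a competing explanation will often be at hand. All patients have cardiovascular disease, all are on preventative therapy, and Section 8.10.1 allows stable lipid-lowering and antiplatelet drugs. A serious bleed in a patient on an antiplatelet drug, or a cardiac event in a patient with coronary disease, may be attributable to either source.

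At stake are the speed with which a DSMB specialist hears of such an SAE and whether it counts in the one SAE measure named for dose selection. Analysis cannot repair this later, because causality is the investigator's opinion recorded on the case report form (9.4.3).

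**Working it through.** The protocol states no figure that depends on this definition, so there is none to reproduce. The check sets the texts side by side, traces where relatedness is used, and then shows what arithmetic can and cannot say about size.

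**1. Does the scale cover an event that drug and background explain about equally well?**

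| Category | Requirement | Met? |
|---|---|---|
| *Related* | clear evidence | No |
| *Possible* | no other explanation, plausible timing | No, another explanation exists |
| *Unlikely/Remote* | an alternative is more likely | No, it is equally likely |
| *Not Related* | ready alternative, and belief that no relationship exists | No, the belief is absent |

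No category fits. The investigator must still choose one, and two of the four are pooled as not related for reporting. Under 9.3.2 the same event is a suspected adverse reaction.

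**2. Where does the rating matter?**

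| Use | Depends on relatedness? |
|---|---|
| DSMB specialist notice of SAEs within 48 hours (3.6, 9.4.1) | Yes |
| DSMB specialist notice of laboratory changes that trigger stopping rules, within 48 hours (3.6) | No |
| Monthly safety data to each DSMB specialist (3.6) | No |
| Quarterly full DSMB review (3.6) | No |
| SAE and special-interest event reports to the Sponsor within 24 hours (9.4.1) | No |
| Dose selection: treatment-related SAE incidence (10.1.4) | Yes |
| Dose selection: platelet reductions, renal or hepatic injury (10.1.4) | No |
| Tables of potentially related events (10.6.2.1) | Yes |
| Tables of all AEs and all serious treatment-emergent AEs (10.6.2.1) | No |

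The stopping rules in 8.6.1 to 8.6.3 are hepatic, renal and platelet rules. A bleeding or cardiac SAE that triggers none of them comes under the 48-hour provision only if it is classed as treatment-related.

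**3. Size.** Each regimen has 45 active patients (10.2). One patient whose SAE moves out of the related group changes that regimen's rate by 1/45 = 0.022, or 2.2 percentage points.

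Anything further needs assumptions. Let *p* be the risk that a patient has a drug-caused SAE and *m* the share of those called unrelated. With independent patients and at most one such SAE each, the chance that a regimen shows at least one SAE classed as related is 1 − (1 − *p*(1 − *m*))^45. The document gives neither value. The 3.8% below is the platelet rate in 10.2, borrowed only as an order of magnitude.

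| *p* | *m* = 0 | 25% | 50% | 75% | 90% |
|---|---|---|---|---|---|
| 2% | 59.7% | 49.3% | 36.4% | 20.2% | 8.6% |
| 3.8% | 82.5% | 72.8% | 57.8% | 34.9% | 15.7% |
| 5% | 90.1% | 82.1% | 68.0% | 43.2% | 20.2% |

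For example, *p* = 3.8% and *m* = 50% give 1 − (1 − 0.019)^45 = 57.8%. With all 225 active patients together and *m* = 50%, the three rows become 89.6%, 98.7% and 99.7%. Within a regimen the loss could be material, but its size rests wholly on *m*.

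**The case against.** The strongest reply is that relatedness is only one of several routes, and the others are open. This stands. A reader might infer that misclassified events vanish from DSMB oversight. They do not: the monthly and quarterly reviews in 3.6 have no causality filter, and stopping-rule laboratory changes go to specialists within 48 hours whatever their cause. What may be lost is early notice of an individual SAE.

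A reader might also infer that the scale hides the platelet, liver and kidney signals that the trial is built to watch. It does not, because 10.1.4 goes on to name those findings as dose-selection considerations without any test of relatedness. That list is introduced as inclusive, so other events are not barred. Bleeding and cardiac SAEs are not named, however, and enter explicitly only through the treatment-related criterion.

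A third tempting inference is that most drug-caused events would be rated unrelated. Nothing in the document supports that. Having a disease or taking a drug does not by itself explain a new event. Lipid-lowering and antiplatelet regimens must have been stable for at least 4 weeks before Screening (5.1), and patients with clearly abnormal transaminases, low eGFR or low platelets are excluded (5.2). Nor does the text force an equal-cause event into an unrelated category. It fits none, and the rating remains the investigator's opinion.

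Finally, 9.2 requires an independent Sponsor assessment and permits upgrading, and 9.4.1 does not say whose assessment counts for the DSMB. This helps only in part. The passage on upgrading is framed around SUSAR status, and 9.4.1 refers to the definitions in 9.4.3.1, so a Sponsor assessor following it meets the same wording.

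**Conclusion.** The point holds in a limited form. The conflict between 9.3.2 and 9.4.3.1 and the missing category are plain on the page and need no assumption. The consequence is conditional: if sites apply the wording literally, some drug-caused SAEs may miss three things, namely the 48-hour specialist notice, the treatment-related SAE criterion and the related-event tables.

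The size is 2.2 percentage points of a regimen's treatment-related SAE rate for each patient reclassified. How many patients that would be is unknown, and the table of chances illustrates assumed values without estimating them. Claims that most events are affected, that events leave DSMB review, or that dose selection as a whole is compromised go beyond the document. A correction is still worthwhile because the contradiction touches both expedited safety reporting and a named dose-selection measure.

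**What to change.** In 9.4.3.1, reword *Possible* to match 9.3.2: the timing is plausible and there is a reasonable possibility that Study Drug caused or contributed to the event, even if another cause could also explain it. Keep *Unlikely/Remote* for events where an alternative is more likely. State that treatment-related in 9.4.1 and 10.1.4, and potentially related in 10.6.2.1, use this definition.

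The cost is one sentence in the protocol, the cross-references and a line in the case report form completion guide. Somewhat more events will be rated possibly related in all arms, including placebo. Because raters are blinded, the pooled placebo group shows how much of that increase is background.

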#### **9.4.3.2 Severity**

The severity of AEs and SAEs will be graded based on criteria from the Common Terminology Criteria for Adverse Events (CTCAE) Version 4.03, June 2010 (refer to [Appendix D](#)). Any AE not listed in Appendix D will be graded as follows:

- **Mild:** The event is easily tolerated by the subject and does not affect the subject's usual daily activities
- **Moderate:** The event causes the subject more discomfort and interrupts the subject's usual daily activities
- **Severe:** The event is incapacitating and causes considerable interference with the subject's usual daily activities

If the event is an SAE, then all applicable seriousness criteria must be indicated (criteria listed in [Section 9.3.3](#)).

#### **9.4.3.3 Action Taken with Study Drug**

Action taken with Study Drug (ISIS 681257 or placebo) due to the event is characterized by 1 of the following.

- **None:** No changes were made to Study Drug (ISIS 681257 or placebo) administration and dose
- **Temporarily Interrupted, Restarted – Same Dose:** Dosing was temporarily interrupted or delayed due to the AE and restarted at the same dose
- **Temporarily Interrupted, Restarted Reduced Dose:** Dosing was temporarily interrupted or delayed due to the AE and restarted at the next lower dose
- **Permanently Discontinued:** Study Drug was discontinued and not restarted

#### **9.4.3.4 Treatment Given for Adverse Event**

Any treatment (e.g., medications or procedures) given for an AE should be recorded on the Adverse Event Case Report Form. Treatment should also be recorded on the concomitant treatment or ancillary procedures eCRF, as appropriate.

#### **9.4.3.5 Outcome of the Adverse Event**

If the event is a non-serious AE, then the event's outcome is characterized by 1 of the following:

- **Ongoing:** Patient terminates from the trial and the AE continues
- **Recovered:** Patient recovered completely from the AE
- **Became Serious:** The event became serious (the date that the event became serious should be recorded as the Resolution Date of that AE and the Onset Date of the corresponding SAE)
- **Change in Severity (if applicable):** AE severity changed

If the event is an SAE, then the event's outcome is characterized by 1 of the following:

- **Ongoing:** SAE continuing
- **Persists (as non-serious AE):** Patient has not fully recovered but the event no longer meets serious criteria and should be captured as an AE on the non-serious eCRF (the SAE resolution date should be entered as the date of onset of that AE)
- **Recovered:** Patient recovered completely from the SAE (the date of recovery should be entered as the SAE resolution date)
- **Fatal:** Patient died (the date of death should be entered as the SAE resolution date)

### **9.5 Procedures for Handling Special Situations**

#### **9.5.1 Abnormalities of Laboratory Tests**

Clinically-significant abnormal laboratory test results may, in the opinion of the Investigator, constitute or be associated with an AE. Examples of these include abnormal laboratory results that are associated with symptoms, or require treatment, e.g., bleeding due to thrombocytopenia, tetany due to hypocalcemia, or cardiac arrhythmias due to hyperkalemia. Whenever possible, the underlying diagnosis should be listed in preference to abnormal laboratory values as AEs. Clinically-significant abnormalities will be monitored by the Investigator until the parameter returns to its baseline value or until agreement is reached between the Investigator and Sponsor Medical Monitor that monitoring is no longer necessary. Laboratory abnormalities deemed not clinically-significant (NCS) by the Investigator should not be reported as AEs. Similarly, laboratory abnormalities reported as AEs by the Investigator should not be deemed NCS on the laboratory sheet.

The Investigator is responsible for reviewing and signing all laboratory reports. The clinical laboratory reports will serve as source documents and should include the Investigator's assessment of clinical significance of out of range/abnormal laboratory values and signatures.

All platelet count results must be reviewed promptly (within 48 hours of receipt) by the Investigator or the designee to ensure that the count has not met the stopping rule and to determine whether the rate of decline is suggestive that the patient could be approaching the dose interruption rule of 75,000/mm^3 as specified in [Section 8.6.3](#).

Any case of a platelet count reduction to levels below 50,000/mm^3 (Grade 3 or Grade 4) is considered an adverse event of special interest and should be reported in an expedited fashion to the Sponsor as per [Sections 9.3.3.1](#) and [9.4.1](#)).

All results of liver function tests must be reviewed promptly (within 48 hours of receipt) by the Investigator or the designee to ensure that the result has not met the stopping rules per [Section 8.6.1](#).

All results of renal function tests must be reviewed promptly (within 48 hours of receipt) by the Investigator or the designee to ensure that the result has not met the stopping rules per [Section 8.6.2](#).

### **9.5.2 Prescheduled or Elective Procedures or Routinely Scheduled Treatments**

A prescheduled or elective procedure or a routinely scheduled treatment will not be considered an SAE, even if the patient is hospitalized; the Study Center must document all of the following:

- The prescheduled or elective procedure or routinely scheduled treatment was scheduled (or was on a waiting list to be scheduled) prior to obtaining the patient's consent to participate in the study
- The condition that required the prescheduled or elective procedure or routinely scheduled treatment was present before and did not worsen or progress in the opinion of the Investigator between the patient's consent to participate in the study and the timing of the procedure or treatment. The condition is documented in the patient's medical history.
- The prescheduled or elective procedure or routinely scheduled treatment is the sole reason for the intervention or hospital admission

